### 6.1. Screening: Visit 1 (Screening Day -125 to -112)

During screening, subjects will be assessed for study eligibility. All screening must be completed and reviewed for subject eligibility before the subject is enrolled into the study. Screening laboratory tests with results considered by the investigator to be transient and inconsistent with the subject's clinical condition may be repeated once during the screening period for confirmation of eligibility. Imaging based examinations for screening must be reviewed before the subject is enrolled to assure an adequate baseline image has been acquired. If the image is determined to be of poor quality, it will be repeated. The visit window (Day -125 to -112) for screening is to allow for the analysis of laboratory testing, assurance of imaging quality and to provide multiple days to perform the assessments in the order described below. As soon as this is completed and subject's eligibility has been confirmed, they may be randomized into the study.

- **Informed Consent:** The subject must sign the informed consent document (ICD) prior to initiation of any screening assessments.
- Demographics: Information such as date of birth, race, and gender will be collected.
- Medical History: Medical history will include confirmation by genetic testing of the diagnosis of LGMD2I as obtained as reported from an appropriate regulated laboratory using a clinically validated genetic test (genetic testing is not provided by the sponsor). Results must confirm the biallelic alteration in the FKRP gene known to be or likely to be pathogenic and associated with LGMD2I. The mutation type will be reported. Medical history will also be reviewed for any significant medical/surgical histories and concurrent illnesses that required or are requiring specialist consultation or treatment.

- **Medication History:** Complete history will include all prescription or nonprescription drugs, and dietary and herbal supplements taken within 28 days prior to the planned first dose.
- Physical Examination, including Nose and Throat Mucosal Exam
- **Pregnancy Test**: A highly sensitive urine pregnancy test will be performed on all women of childbearing potential (WOCBP).
- **Diary Cards:** Will be provided with instructions to all WOCBP to record the first day of each menstruation cycle.
- Contraception Review: Confirmation of use of acceptable forms of contraception.
- Weight
- Vital Signs: Supine blood pressure, pulse rate, respiratory rate, and oral temperature.
- **12-lead ECG:** ECGs will be performed in triplicate.
- Echocardiogram
- Clinical laboratory testing:
  - Hematology with complete blood count and differential, comprehensive metabolic panel (sodium, potassium, chloride, carbon dioxide, blood urea nitrogen, creatinine, calcium, glucose, total protein, albumin, total bilirubin, AST, ALT, alkaline phosphatase) gamma-glutamyl transferase (GGT), prothrombin time (PT), activated partial thromboplastin time (aPTT), creatine kinase, amylase, cardiac troponin I. Urinalysis.
- Serum ferritin, serum iron, % transferrin saturation, TIBC: fasting blood collection
- Horomone Testing: LH, FSH, estrogen in WOCBP
- GLDH
- **Fecal Occult Blood:** Fecal sample is to be collected at home within 1 week of scheduled visit and mailed to site for testing.
- C-SSRS
- MRI-liver: Liver MRI will be obtained for iron accumulation
- Inclusion/Exclusion Criteria: Subjects will be assessed against inclusion and exclusion criteria.

• **Enrollment:** Enrollment can be performed once all screening results are available and eligibility is confirmed

## 6.2. Lead-in Period: Visit 2 (Baseline Day -111 to -110 prior to dosing on Day 1)

The following procedures and studies should be performed in the morning (before noon) of Visit 2 whenever possible

- Physical Examination, including Nose and Throat Mucosal Exam
- **Pregnancy Test**: A highly sensitive urine pregnancy test will be performed on all female subjects and must be confirmed as negative within 1 month of receiving first dose.
- Diary Cards: For collection of first day of each menstrual cycle for WOCBP.
- Contraception Review: Confirmation of use of acceptable forms of contraception
- Height: Height should be measured in the morning.
- Weight
- Vital signs: Supine blood pressure, pulse rate, respiratory rate, and oral temperature.
- Horomone Testing: LH, FSH, estrogen in WOCBP
- GLDH
- C-SSRS
- **MRI-muscle:** WB-MRI and dedicated thigh MRI will be performed for muscle quantity and quality

The following procedures should be performed in the afternoon of Visit 2 whenever possible:

- **DXA:** Whole body DXA will be performed for lean body mass.
- **Functional assessments:** Must be conducted in the following order: Respiratory function (FVC, FEV1, MIP, MEP), 4SC, 2MWT, 10-meter walk/run, TUG, strength assessment (MMT, hand-held dynamometry) and PUL.
- **Needle muscle biopsy:** Following WB-MRI and functional assessments a needle muscle biopsy of the tibialis muscle will be performed.
- PD sample collection

- **Biomarker collection:** Blood will be collected for proteomic, metabolomic, and genomic biomarker analysis
- Adverse event monitoring
- Concommitant medications

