Visit Number (Study Day Visit Window) a	1 (-125 to -112)	2 (-111 to -110)	3 (1)	4 (29 ± 3)	5 (57 ±3)	6 (85 ±3)	7 (113 ±3)	8 (141 ±3)	9 (169 ±3)	10 (197 ±3)	11 (225 ±3)	12 (337 ±3)	
Biomarkers collection m		Х					Х			Х			
Adverse event monitoring		X	Х	Х	Х	Х	X	Х	X	Х	Х	X	Х
Infusion site reaction			Х	Х	X	Х	X	Х	Х	Х	Х		Х
Concomitant medications		X	Х	X	X	Х	X	Х	Х	Х	Х	Х	Х

Abbreviations: 2MWT=Two minute walk test; 4 SC= Four stair climb, C-SSRS=Columbia Suicide Severity Rating Scale, DXA=Dual-energy x-ray absorptiometry; ECG = electrocardiogram; FSH= Follicle stimulating hormone; FVC=Forced vital capacity; FEV1 = Forced expiratory voume in 1 second; GLDH=glutamate dehydrogenase, LH-Lutenizing hormone, MIP= Mean inspiratory pressure; MEP= Mean expiratory pressure; MMT= manual muscle testing, MRI=magnetic resonance image; PD=Pharmcodynamics, PK=Pharmocokinetics, PUL=Performance of Upper Limb, TIBC=Total iron binding capacity, INQoL = Individualized Neuromuscular Disease Quality of Life, SF-36 = Short Form 36 Health Survey

- a. Assessments should be conducted on the Study Day within the visit window. Visits with MRI, DXA and functional assessments may be conducted over 2 days. The following order of testing is preferred. On the first day of assessments: an am fasting blood collection followed by fasting DXA and MRI. On the second day of assessments: the functional assessments and muscle biopsy. Whenever possible, functional testing and MRI should occur prior to biopsy. Depending on the timing of enrollment and evaluation of safety in the 20 mg/kg dose (Cohort 2), the dose escalation of Cohort 1 to 40 mg/kg may be delayed. Subjects in Cohort 1 will only receive 8 doses of the 5 mg/kg dose and not proceed to the 40 mg/kg dose until review by the SMC. In addition, depending on the timing of enrollment and evaluation of safety in the 5 mg/kg dose (Cohort 1), the Lead-In period for Cohort 2 may be extended prior to initiation of treatment phase.
- b. Medical history will include confirmation by genetic testing of the diagnosis of Limb Girdle Muscular Dystrophy (LDMG2I) as obtained from an approved laboratory. Results must confirm the presence of a biallelic alteration in the FKRP gene known or likely to be pathogenic.
- c. Enrollment can be performed once all screening results are available and eligibility is confirmed.

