## 6. STUDY PROCEDURES

Every attempt should be made to schedule the visits on the day specified in the Schedule of Activities. In order to provide optimal testing conditions and consistency in endpoint measurements, at visits when the functional assessments, imaging and clinical laboratory assessments are scheduled to be completed at the same visit, the visit should be completed on two days within the visit window and at approximately the same time of day in the order described below.

There is no window for Day 1(first dosing day). The visit window for the additional treatment visits is  $\pm 3$  Day. For the final follow up visit, the window is  $\pm 3$  days. The window for the PK assessments post dosing at 2 hours is  $\pm 30$  minutes. If the infusion rate is decreased (following an infusion site reaction) the PK/PD assessment should be collected at the time of infusion completion and flush (within a  $\pm 30$  minute window). Subjects are required to be observed for 1 hour after administration of PF-06252616.

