# 7.6.3. Duel-energy X-ray Absorptiometry (DXA) and X-ray

#### 7.6.3.1. DXA

DXA scans will be obtained according to the Schedule of Activities to measure the percent change in lean body mass (LBM) over time and to evaluate bone mineral density (BMD) on the spine and hip. Ideally, whole body scans will be taken at approximately the same time of day (morning) and subjects will have fasted for at least 4 hours prior to the scan, but should be in a state of euhydration.

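### Protocol 6.2 places the Visit 2 whole-body DXA in the afternoon while 7.6.3.1 prefers a fasted morning scan, so the lead-in change in lean mass may be confounded with time of day

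*Protocol*

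**What the plan says.** Protocol 6.2 splits Visit 2 into a morning list and a second list headed "The following procedures should be performed in the afternoon of Visit 2 whenever possible". Muscle MRI is on the morning list. The second list begins with DXA: "Whole body DXA will be performed for lean body mass".

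Two other places describe the same scan differently:

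- Section 7.6.3.1: "Ideally, whole body scans will be taken at approximately the same time of day (morning"), and in the same sentence "subjects will have fasted for at least 4 hours prior to the scan".
- Schedule of Activities, footnote a: "The following order of testing is preferred", and then, for the first of two assessment days, "an am fasting blood collection followed by fasting DXA and MRI". Functional tests and biopsy follow on the second day.

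Section 4.4.1 sets a fasting rule for any DXA scan: 4 hours without food or, failing that, no big meal. Sections 6.3, 6.8 and 6.9, which cover the later whole-body scans, give no time of day.

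**The concern.** A site that follows the visit-specific text at Visit 2 and the general DXA text elsewhere will scan Visit 2 in the afternoon and Visit 3 onward in the morning. The two ends of the lead-in interval are then measured under different conditions.

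The lead-in is there to show each subject's own progression before treatment (protocol 3.1), and the design rationale in 1.11 compares change before, during and after treatment. There is no concurrent control. For lean mass, Visit 3 minus Visit 2 is the only change observed off drug before any exposure. A measurement shift that falls mainly on Visit 2 has the same sign in every affected subject, so averaging over the planned 20 subjects does not remove it.

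**Working it through.** The plan states no figure to reproduce: it gives no standard deviation, time-of-day effect or sample-size basis for DXA lean mass. The check compares the texts and then uses simple algebra.

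**Time of day**

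- Visit 2: 6.2 says afternoon, 7.6.3.1 says morning. These conflict directly.
- Visit 3, Cohort 1 Visit 11 and the two follow-up visits: 6.3, 6.8 and 6.9 are silent, so the morning preference in 7.6.3.1 is the only guidance.
- Section 6 asks for visits "at approximately the same time of day in the order described below". That sentence is written for visits combining function tests, imaging and clinical laboratory tests. The schedule marks no clinical laboratory tests at Visit 2, so it does not clearly settle the matter.

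**Fasting state**

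- The rule in 4.4.1 is tied to the scan, not to the clock, and nothing exempts Visit 2.
- Visit 3 and the follow-up visits include an iron panel, which footnote g wants drawn in the morning after 8 hours' fasting. Visit 2 has no iron panel.
- The biomarker blood at Visit 2, which 7.2.1 wants in the morning after an 8-hour fast, is also on the afternoon list in 6.2.
- So the later DXA visits bring subjects in fasted by design, while an afternoon Visit 2 scan relies on 4.4.1 alone. This is a risk of different fasting states and does not show that they differ.

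**Effect on the lead-in change**

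Let d be the true percent change over the lead-in, and let an afternoon scan read b% differently from a morning scan of the same person. With Visit 2 in the afternoon and Visit 3 in the morning:

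observed change = 100 × [(1 + d/100) / (1 + b/100) − 1] ≈ d − b

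The documents give neither the size nor the sign of b. Purely as an assumed range, with d = 0:

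- b = 0.5: 100 × (1/1.005 − 1) = −0.50 points
- b = 1: 100 × (1/1.01 − 1) = −0.99 points
- b = 2: 100 × (1/1.02 − 1) = −1.96 points

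A negative b reverses the sign. If only a fraction p of subjects have mismatched scans, the mean shift is about −p × b; for example, p = 0.5 and b = 1 give −0.5 points. If Visits 2 and 3 are scanned at the same time of day and in the same fasting state, the shift is zero.

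**Where it travels**

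Change measured from Visit 3 does not use the Visit 2 scan, so it carries no shift from this source. A contrast of on-treatment change minus lead-in change would shift by about +b.

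**The case against.** The strongest reply is that these are soft preferences. Section 7.6.3.1 describes an ideal, footnote a a preferred order, and 6.2 what to do where possible. In footnote a the morning attaches to the blood draw, with the DXA merely following it. This stands: a reader might infer that the protocol requires a morning scan, and it does not. It remains true that the preferences point different ways for the same scan.

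Second, the mismatch is conditional. Section 6.3 sets no hour for Visit 3 and lists DXA after a muscle MRI session of about 2 hours (7.6.2), so that scan could also slip past noon. This stands too. One cannot say that all 20 subjects are affected.

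Third, 4.4.1 already controls food intake. This stands as far as it goes. A reader might infer that subjects will have eaten before the Visit 2 scan, and might size the bias by dividing an assumed mass of food and drink by lean mass. The documents do not support this: they apply the fast, or at least the no-big-meal rule, to every scan, ask for normal hydration at whole-body scans, and give no intake figure.

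Fourth, the planned analysis makes little use of the Visit 2 scan. Lean mass is exploratory (protocol 2.2.3.1) and SAP 8.2.5.1 only summarises such endpoints. The pooled lead-in comparison in SAP section 8 is set out for secondary endpoints, and the model in SAP 8.2.2 does not list DXA. SAP 6.2.3 takes the last pre-dose value as baseline for pharmacodynamic endpoints, which would be Visit 3. This largely stands and limits the severity. Two loose ends remain: protocol 9.2.2 names imaging endpoints for the mixed model, and the title of 6.2 labels Visit 2 as baseline.

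**Conclusion.** The inconsistency is real and minor. Section 6.2 steers the Visit 2 whole-body DXA to the afternoon, while 7.6.3.1 and footnote a favour a fasted scan in the morning or straight after the morning blood draw. If each is followed where it applies, the trial's only untreated lean-mass change is confounded with time of day. Confounding with fasting state is possible but not established.

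The size is unknown: about −b points for a b% shift at Visit 2, in proportion to the share of subjects with mismatched scans, and zero if the scans match. A reader might infer that the on-treatment gain is made to look better. That does not follow for change measured from Visit 3; it would arise only in a contrast with the lead-in change, and only if b is positive. Setting any such shift against the 4.48% quadriceps figure quoted from the healthy-volunteer study would also mislead, because that is MRI muscle volume and not DXA lean mass.

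**What to change.** Move whole-body DXA in 6.2 from the afternoon list to the morning list, fasted as in 7.6.3.1 and footnote a, so that Visits 2 and 3 match. Reconcile the Visit 2 biomarker draw with 7.2.1 in the same edit. Record scan clock time and hours fasted at every whole-body DXA.

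For scans already done, list clock times where available. Show the lead-in lean-mass change separately for subjects whose Visit 2 and Visit 3 scans were and were not at a similar time of day. Do not simply drop afternoon Visit 2 scans: if 6.2 was followed, that could remove most of the lead-in data.

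The cost is two CRF fields and a tighter Visit 2 morning, since muscle MRI is already there. The two-day window for Visit 2 (Day -111 to -110) gives room to spread the work. No extra procedure is needed.

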### 6.3. Active Treament Period: Visit 3 (Day 1) and for Cohort 1, Visit 11 (Day 225±3)

Visit 3 will be divided into a 2 day visit

#### **Prior to dosing, the following procedures will be completed:**

- Physical Examination, including Nose and Throat Mucosal Exam
- **Pregnancy Test**: A highly sensitive urine pregnancy test will be performed on all female subjects
- Diary Cards: For collection of first day of each menstrual cycle for WOCBP.
- Contraception Review: Confirmation of use of acceptable forms of contraception
- Weight
- Vital signs: Supine blood pressure, pulse rate, respiratory rate, and oral temperature.
- **12-lead ECG:** ECGs will be performed in triplicate
- Clinical laboratory tests:
  - Hematology with complete blood count and differential, comprehensive metabolic panel (sodium, potassium, chloride, carbon dioxide, blood urea nitrogen, creatinine, calcium, glucose, total protein, albumin, total bilirubin, AST, ALT, alkaline phosphatase) gamma-glutamyl transferase (GGT), prothrombin time (PT), activated partial thromboplastin time (aPTT), creatine kinase, amylase, cardiac troponin I. Urinalysis.
- Serum ferritin, serum iron, % transferrin saturation, TIBC: fasting blood collection
- Horomone Testing: LH, FSH, estrogen in WOCBP
- GLDH
- **Fecal occult blood**: Fecal sample is to be collected at home within 1 week prior to scheduled visit.
- C-SSRS

- Immunogenicity: Baseline
- PD sample collection: Predose
- PK sample collection: Predose
- **MRI-liver**: Liver MRI will be obtained for iron accumulation (visit 11 only)
- **MRI-muscle:** WB-MRI and dedicated thigh MRI will be performed for muscle quantity and quality
- **DXA Whole Body:** Whole body DXA will be performed for lean body mass.
- **DXA Spine and Hip:** Spine and hip DXA will be performed for BMD.
- **Functional assessments:** Must be conducted in the following order: Respiratory function (FVC, FEV1, MIP, MEP), 4SC, 2MWT, 10-meter walk/run, TUG, strength assessment (MMT, hand-held dynamometry) and PUL.
- Quality of Life assessments
  - InQol
  - SF-36

#### On Day 2 of Visit 3 (Day 1)- prior to dosing,

- **Functional assessments:** Must be conducted in the following order: 4SC, 2MWT, 10-meter walk/run, TUG, and PUL.
- **Needle muscle biopsy:** Following the Functional assessments, a needle muscle biopsy of the tibialis muscle will be performed.

#### Dosing

• Study treatment administration.

#### After dosing, the following procedures will be completed:

- Vital signs: Supine blood pressure, pulse rate, respiratory rate, and oral temperature after completion of infusion.**PK sample collection**: Collected at end of infusion (hour 2)
- **PD sample collection**: Collected at end of infusion (hour 2)
- Infusion site reaction monitoring.
- Adverse event (AE) monitoring.

• Concomitant medication monitoring.

# 6.4. Active Treatment: Visit 4 (Day 29±3), 8 (Day 141±3), 10 (Day 197±3) and for Cohort 1, Visit 12 (Day 253±3), 16 (Day 365±3), 18 (Day 421±3)

- **Pregnancy Test**: A highly sensitive urine pregnancy test will be performed on all female subjects
- Diary Cards: For collection of first day of each menstrual cycle for WOCBP.
- Contraception Review: Confirmation of use of acceptable forms of contraception
- Weight
- Vital Signs: Supine blood pressure, pulse rate, respiratory rate, and oral temperature.
- Clinical laboratory testing:
  - Hematology with complete blood count and differential, comprehensive metabolic panel (sodium, potassium, chloride, carbon dioxide, blood urea nitrogen, creatinine, calcium, glucose, total protein, albumin, total bilirubin, AST, ALT, alkaline phosphatase) gamma-glutamyl transferase (GGT), prothrombin time (PT), activated partial thromboplastin time (aPTT), creatine kinase, amylase, cardiac troponin I. Urinalysis.
- Serum ferritin, serum iron, % transferrin saturation, TIBC: fasting blood collection
- Horomone Testing: LH, FSH, estrogen in WOCBP
- GLDH
- **Fecal Occult Blood:** Fecal sample is to be collected at home within 1 week prior to scheduled visit.
- C-SSRS

#### Dosing

• Study treatment administration.

#### After dosing, the following procedures will be completed:

- Vital signs: Supine blood pressure, pulse rate, respiratory rate, and oral temperature after completion of infusion. Infusion site reaction monitoring.
- AE monitoring.

• Concomitant medication monitoring.

# 6.5. Active Treatment: Visit 5 (Day 57±3), 9 (Day 169±3) and for Cohort 1, Visit 13 (Day 281±3), 17 (Day 393±3)

- **Pregnancy Test**: A highly sensitive urine pregnancy test will be performed on all female subjects
- Diary Cards: For collection of first day of each menstrual cycle for WOCBP.
- Contraception Review: Confirmation of use of acceptable forms of contraception
- Weight
- Vital Signs: Supine blood pressure, pulse rate, respiratory rate, and oral temperature.
- Clinical laboratory testing:
  - Hematology with complete blood count and differential, comprehensive metabolic panel (sodium, potassium, chloride, carbon dioxide, blood urea nitrogen, creatinine, calcium, glucose, total protein, albumin, total bilirubin, AST, ALT, alkaline phosphatase) gamma-glutamyl transferase (GGT), prothrombin time (PT), activated partial thromboplastin time (aPTT), creatine kinase, amylase, cardiac troponin I. Urinalysis.
- Serum ferritin, serum iron, % transferrin saturation, TIBC: fasting blood collection
- Horomone Testing: LH, FSH, estrogen in WOCBP
- GLDH
- **Fecal Occult Blood:** Fecal sample is to be collected at home within 1 week prior to scheduled visit.
- C-SSRS
- PK/PD sample: predose

#### Dosing

• Study treatment administration.

#### After dosing, the following procedures will be completed:

• Vital signs: Supine blood pressure, pulse rate, respiratory rate, and oral temperature at - after completion of infusion.

- **PK/PD sample collection**: Collected at end of infusion (hour 2)
- Infusion site reaction monitoring.
- AE monitoring.
- Concomitant medication monitoring.

6.6. Active Treatment: Visit 6 (Day 85±3) and for Cohort 1, Visit 14 (Day 309±3)

- Physical Examination, including Nose and Throat Mucosal Exam.
- **Pregnancy Test**: A highly sensitive urine pregnancy test will be performed on all female subjects
- Diary Cards: For collection of first day of each menstrual cycle for WOCBP.
- Contraception Review: Confirmation of use of acceptable forms of contraception
- Weight
- Vital signs: Supine blood pressure, pulse rate, respiratory rate, and oral temperature.
- 12 lead ECG: ECGs will be performed in triplicate
- Clinical laboratory sample collection:
  - Hematology with complete blood count and differential, comprehensive metabolic panel (sodium, potassium, chloride, carbon dioxide, blood urea nitrogen, creatinine, calcium, glucose, total protein, albumin, total bilirubin, AST, ALT, alkaline phosphatase) gamma-glutamyl transferase (GGT), prothrombin time (PT), activated partial thromboplastin time (aPTT), creatine kinase, amylase, cardiac troponin I. Urinalysis.
- Serum ferritin, serum iron, % transferrin saturation, TIBC: fasting blood collection
- Horomone Testing: LH, FSH, estrogen in WOCBP
- GLDH
- **Fecal Occult Blood:** Fecal sample is to be collected at home within 1 week prior to scheduled visit.
- C-SSRS
- MRI of liver: Liver MRI will be obtained for iron accumulation

